#### 2 FLOW CHART AND VISIT SCHEDULE

### 2.1 Double blind Period

#### 2.2 **Open Label Extension**

\*Week 5 visit required only for subjects who received placebo + ADT during the double-blind period

Study Day	Screening Visit	1	29	85 and Every Subsequent 84 Days	Safety Follow-up	Unscheduled	Long Term Follow-up‡
Study Week	-4 to -1 (28 Days)	1	5	13 and Every Subsequent 12 Weeks	30 Days after Last Dose§	Visit†	Every 12 Weeks
Window (Days)			± 5	± 5	± 7	NA	± 7
Informed Consent	Х						
Medical History	Х						
Inclusion/Exclusion Criteria	Х	Х					
Randomization (IRT)		Х					
Vital Signs	Х	Х	Х	Х	Х	Х	
Physical Examination including Weight	Х	Х	Х	Х	Х	Х	
Height	Х						
12-lead Electrocardiogram	Х	Х			Х		
Clinical Labs ††	Х	Х	Х	Х	Х	Х	
Prostate-specific antigen	Х	Х	Х	Х	Х		
Sample for Genotyping Analysis ‡‡		Х					
CCI		Х		Х			
Testosterone				Х			
CT/MRI and Bone Scan§§, ¶¶	X§§			X¶¶			Х
Chest X-ray or Chest CT/MRI †††	Х			Х			Х
ECOG Performance Status	Х	Х	Х	Х	Х	Х	
QoL Assessment (QLQ-PR25, EQ-5D-5L, FACT-P,		v		v	v		$\mathbf{V}^{\mathbf{+}}$
BPI-SF)		Л		Λ	Λ		Λ.
Adverse Events§§§	Х	Х	Х	X	Х	Х	
Previous and Concomitant Medications	Х	Х	Х	X	Х	Х	
Study Drug Dispensing		Х	Х	X			
Study Drug Treatment		Х	Х	Х			

#### Table 1Double-Blind Period Schedule of Assessments

CT: computed tomography; ECOG: Eastern Cooperative Oncology Group; EQ-5D-5L: EuroQol Group-5 Dimension-5 Level Instrument; IRT: Interactive Response Technology; MRI: magnetic resonance imaging; NA: not applicable; FACT-P: Functional Assessment of Cancer Therapy-Prostate; QLQ-PR25: Quality of Life Prostate-specific Questionnaire; QoL: quality of life; BPI-SF: Brief Pain Inventory-Short Form

† Unscheduled visits may be performed at any time during the study whenever necessary to assess for or follow-up on adverse events at the patient's request or if deemed necessary by the Investigator. Procedures and assessments are to be performed as clinically indicated. Testosterone testing through central laboratory at unscheduled visit requires prior approval by sponsor.

Footnotes continued on next page

SAP Final Version 1.0

#### Sponsor: Astellas Pharma Global Development, Inc

ISN/Protocol 9785-CL-0335

- ‡ After study drug discontinuation, all patients MUST undergo long term follow-up. Long term follow-up assessments will include monitoring for survival status, new antineoplastic therapies for prostate cancer, and symptomatic skeletal events. Follow-up may be conducted by telephone interview. Patients will continue to be scanned every 12 weeks until radiographic progression is confirmed by independent review or the number of radiographic progression-free survival events is reached. For patients continuing with radiographic assessments, if seen in clinic, QoL assessment will also be completed until the initiation of new antineoplastic therapy for prostate cancer or the number of progression events is reached. Additional follow-up contacts may be requested. Patients will be followed for overall survival until death, lost to follow up, overall survival final analysis or termination of the study by the sponsor.
- § Or prior to initiation of new antineoplastic therapy for prostate cancer, whichever occurs first.
- A brief physical examination is required at each visit, with the exception of the screening visit during which a complete physical examination will be completed.
- †† Laboratory assessments include serum chemistries and hematology.
- ‡‡ Genotyping samples will only be collected from patients who agree to provide genotyping samples as documented by signing a separate genotyping informed consent form (ICF).

CCI

- ∬
- §§ The abdominal-pelvic CT scan or MRI, bone scan, chest x-ray or chest CT must occur within 6 weeks of day 1; otherwise the screening visit assessment must be repeated. Radiographic assessments performed prior to informed consent, as part of the routine care, may be used as the baseline assessment if performed within 6 weeks of day 1 and if digital format images are available for submission to the sponsor-designated independent central review facility.
- The window for all radiographic (CT/MRI) assessments is ± 7 days. For patients who discontinue study treatment without radiographic progression, confirmed by central review, patients will continue to be scanned every 12 weeks until radiographic progression is confirmed by independent review or the number of radiographic progression-free survival events is reached.
- ††† Chest CT is required at all imaging time points if screening chest x-ray demonstrates metastatic chest disease.
- §§§ Adverse events will be collected from the time the patient signs the ICF until the end of the safety reporting period (or until screen failure). The safety reporting period ends at the time of the safety follow-up visit, 30 days after last dose of study drug or initiation of new antineoplastic therapy for prostate cancer.

Table 2	Open-Label	Extension	Schedule	of Assessments
---------	-------------------	-----------	----------	----------------

Study Period or Visit	OL Treatment			Unscheduled Visit	OL Safety Follow-up	OL Long Term Follow-up
Study Week	OL 1  (Day 1)	OL 5  (Day 29)	OL 13 and every subsequent 12 weeks (Day 85 and every subsequent 84 days)	Varies 	30 Days after Last Dose 	Every 12 Weeks
Window (Days)	NA	± 3	± 5	NA	± 7	± 7
Informed Consent 	X					
Inclusion/Exclusion Criteria for OLE	X					
Open-Label Enrollment (via IRT)	X					
Brief Physical Examination	X		Х	Х	Х	
Vital Signs including Weight	X	Х	Х	Х	Х	
ECOG Performance Status	X	Х	Х	Х	Х	Х
12-lead Electrocardiogram	X				X	
Clinical Labs (including PSA)	X	Х	Х	Х	Х	
CCI	X 		X 			
Radiographic Assessments'	Х		Х			Х
QoL Assessment (QLQ-PR25, EQ-5D-5L, FACT-P, BPI-SF)	Х		Х		Х	Х
Adverse Events 	Х	Х	Х	Х	Х	
Concomitant Medication Review	Х	Х	Х	Х	Х	
Study Drug Dispensing (via IRT)	X	Х	Х			
Study Drug Accountability	X	X	X		X	
Long-Term Follow-up Assessments 						X

ECOG: Eastern Cooperative Oncology Group; EQ-5D-5L: Euro Qol Group-5 Dimension-5 Level Instrument; FACT-P: Functional Assessment of Cancer Therapy-Prostate; IRT: Interactive Response Technology; OL: Open-Label; OLE: Open-Label; Extension; QLQ-PR25: Quality of Life Prostate-specific Questionnaire; QoL: Quality of Life.

1 For subjects previously receiving placebo, Open-Label (OL) Day 1/Week 1 should occur within approximately 16 weeks after the approval and activation of this protocol at the study site and no later than 6 weeks after screening. For subjects continuing treatment with enzalutamide, OL Day 1/Week 1 will be their next regular scheduled visit following approval and activation of this protocol at the study site.

CCI

2 Only for subjects starting new treatment with enzalutamide (previously received placebo).

3 As necessary to assess or follow up adverse events.

4 Prior to initiation of new antineoplastic therapy for prostate cancer, or 30 days after last dose of enzalutamide, whichever occurs first.

5 Informed consent must be obtained before performing any study-specific procedures on Day 1/Week 1 for all subjects participating in OL Period.

6

7 For subjects who have not progressed radiographically, scans (CT/MRI and bone scan) will be performed every 12 weeks for the first year on enzalutamide and then every 24 weeks until the subject has progressed radiographically, as assessed by local read.

8 Adverse events will be collected from the time the subject signs the consent form until screen failure or through safety follow-up visit (prior to initiation of new antineoplastic therapy for prostate cancer, or 30 days after last dose of enzalutamide, whichever occurs first).

9 Long-term follow-up assessments include survival status, symptomatic skeletal events and new antineoplastic therapies for prostate cancer. May be obtained by telephone contact, chart review or clinic visit.

18 July 2021

## **3** STUDY OBJECTIVE(S) AND DESIGN

## 3.1 Study Objective(s)

Refer to the study protocol for a full list of study objectives.

Efficacy objective in the open label extension period is to determine the benefit of enzalutamide plus ADT as compared to placebo plus ADT as assessed by overall survival (OS). Additionally, time to new antineoplastic therapy will be summarized descriptively as supportive information in the evaluation of the overall survival endpoint.

Safety objective is to determine the safety of enzalutamide plus ADT as compared to placebo plus ADT.

## 3.2 Study Design

This is a multinational phase 3, randomized, double-blind, placebo-controlled efficacy and safety study of enzalutamide plus ADT versus placebo plus ADT in patients with mHSPC. After the double-blind period has completed, eligible patients were allowed to received open label enzalutamide in an open label extension period.

Approximately 1100 subjects were randomized centrally 1:1, and the randomization was stratified by volume of disease (low versus high) and prior docetaxel therapy for prostate cancer (no prior docetaxel, 1-5 cycles, 6 cycles). High volume of disease is defined as metastases involving the viscera or, in the absence of visceral lesions, there must be 4 or more bone lesions, at least 1 of which must be in a bony structure beyond the vertebral column and pelvic bone. Prior docetaxel therapy is defined as 1 or more cycles of docetaxel but no more than 6 cycles.

In this study, patients received 4 capsules of enzalutamide (40 mg each) or placebo per day orally in the double-blind period. After the double-blind period has completed, eligible patients received 4 capsules of enzalutamide (40 mg each) in the open label extension period. As long as the patient is tolerating the study drug, the treatment should be continued until radiographic disease progression (rPD) or starting an investigational agent or new therapy for treatment of prostate cancer. Patients who discontinue study drug without radiographic progression will continue to follow the radiographic assessment schedule until radiographic progression event or until the target number of deaths is reached for the final analysis of OS.

The following assessments of prostate cancer status will be collected during OLE: soft tissue disease on CT scan or on MRI, bone disease on radionuclide bone scans, survival status, EQ-5D-5L, QLQ-PR25, FACT-P for QoL and BPI-SF for pain symptom assessment. Throughout the study, safety and tolerability were assessed by the recording of adverse events (AE), vital signs, physical examinations, 12-lead electrocardiograms (ECG), and safety laboratory evaluations (including PSA).

Patients will have a safety follow-up visit 30 days after their last dose of study drug or prior to initiation of new antineoplastic therapy for prostate cancer, whichever occurs first. All

patients are to be followed for survival until death, loss to follow-up, withdrawal of consent, or study termination by the sponsor. All patients will be followed until the final OS analysis.

## 3.3 Randomization

Subjects were entered into the Interactive Response Technology system (IRT) at screening and assigned a subject number.

After the double-blind period, which included random assignment to enzalutamide or placebo (stratified by prior docetaxel use and disease volume), eligible patients were allowed to received open label enzalutamide, as recorded in the IRT system.

## 4 SAMPLE SIZE

For OS, 342 death events will be required to provide 80% power to detect a target HR of 0.73 with a target difference in Kaplan-Meier estimated median of approximately 15 months (40 months for placebo versus 55 months for enzalutamide) at the 4% significance level under the assumption of an exponential distribution. This significance level was chosen to apply a parallel testing strategy between OS and other key secondary endpoints (with allocated type I error rate of 1%) as described in section 7.4.1.

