## **1 INTRODUCTION**

A Statistical Analysis Plan (SAP) contains a more technical and detailed elaboration of the principal features of the analysis described in the protocol and includes detailed procedures for executing the statistical analysis of the primary and secondary endpoints and other data. This SAP contains details related to analyses specific to the Open Label Extension Period (OLE), in addition to the SAP (version 3.0) used for the primary analysis.

The SAP is finalized and signed prior to database hard lock to ensure lack of bias. If needed, revisions to the approved SAP may be made prior to database hard lock. Revisions will be version controlled.

This statistical analysis is coordinated by the responsible biostatistician of Astellas Pharma. Any changes from the analyses planned in the SAP will be justified in the Clinical Study Report.

Prior to database hard lock, a final blinded review of data and TLFs meeting will be held to allow a review of the clinical trial data and to verify the data that will be used for any new analysis set classification. If required, consequences for the statistical analysis will be discussed and documented. A meeting to determine analysis set classifications may also be held prior to database hard lock.

This SAP for the open-label extension is a supplement to the main study SAP which was completed prior to unblinding the study. The methods for the analysis of overall survival were established in the main study SAP. This SAP includes those methods and adds sensitivity and subgroup analyses for overall survival and an updated analysis for time to new antineoplastic. This SAP also describes the planned summaries for safety, disposition, and other data to incorporate the placebo patients who crossed over to open-label enzalutamide.

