## 5 ANALYSIS SETS

#### 5.1 Intent-to-Treat Population

The Intent-to-Treat (ITT) population is defined as all subjects who were randomized in this study. The ITT population will be analyzed by treatment arm as randomized, (i.e., treatment arm by randomization assignment) regardless of whether or not study drug was administered. The ITT population will be used to conduct efficacy analyses, unless otherwise specified.

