#### 6.3 Treatment Emergent Adverse Event (TEAE)

A TEAE is defined as an AE that occurs or worsen at any time during the treatment emergent period. The treatment emergent period is time interval encompassing the double-blind treatment emergent period and the OLE treatment emergent period.

The double-blind treatment emergent period is defined as the time interval from the first double-blind study drug intake up to 30 days after the date of the last dose of double-blind study drug, study discontinuation, the start of new antineoplastic therapy, or the first dose of OLE treatment, whichever occurs first.

If AE start date is the same date as the study start, then it will be considered as a TEAE if the box 'Onset after first dose of study' is ticked in the Electronic case report form(eCRF). If a patient experiences an event both during the pre-investigational period and during the investigational period, the event will be considered as TEAE only if it has worsened in severity (i.e. it is reported with a new start date).

The OLE treatment emergent period is defined as the time interval from the OLE study drug intake up to 30 days after the date of the last dose of OLE study drug, study discontinuation, or the start of new antineoplastic therapy, whichever occurs first.

AE with both a missing start and stop dates, and AEs with a missing start date but has a known stop date which is on or after the first dose of study drug will be considered treatment-emergent.

For each treatment group, the treatment emergent period is as follows;

- Enzalutamide group: from the first DBT study drug intake up to 30 days after the date of the last dose of study drug, study discontinuation, or the start of new antineoplastic therapy, whichever occurs first.
- Placebo group: from the first DBT study drug intake up to 30 days after the date of the last dose of placebo, start of open-label enzalutamide, study discontinuation, or the start of new antineoplastic therapy, whichever occurs first.
- Placebo crossover group: from the first OLE study drug intake up to 30 days after the date of the last dose of OLE study drug, study discontinuation, or the start of new antineoplastic therapy, whichever occurs first.

AEs will be coded to System Organ Class (SOC) and preferred term using MedDRA v23.0 and severity graded using National Cancer Institute's Common Terminology Criteria version 4.03 (NCI-CTCAE v4.03) for AEs.

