#### 7.4.1 Overall Survival

At the time of the primary analysis of rPFS, the interim analysis of OS was not significant (84 deaths from any cause, 39 in Enzalutamide + ADT group and 45 in Placebo + ADT group, p=0.3361 from stratified log-rank test). The final analysis of OS will be conducted when approximately 342 events (death from any cause) have occurred.

At the time of the primary analysis of rPFS, the following six key secondary endpoints were tested: OS, Time to PSA progression, time to initiation of a new antineoplastic therapy, the rate of PSA decline to <0.2ng/mL (PSADecR), objective response rate and the time to deterioration in urinary symptoms from the QLQ-PR25. To maintain the family-wise 2-sided type I error rate at 0.05, a parallel testing strategy between OS (with allocated type I error rate 0.04) and the other five endpoints (with allocated type I error rate 0.01) was performed, as summarized in Figure 1.

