#### Figure 1 Testing Strategy for the Primary and Six Selected Secondary Endpoints

rPFS: radiographic progression-free survival; OS: overall survival; TTPP: time to PSA progression; TTNAnti: time to initiation of a new antineoplastic therapy; PSADecR: rate of PSA decline to <0.2 ng/mL; ORR: objective response rate; TTUri: the time to deterioration in urinary symptoms from the QLQ-PR25 \*OS will be tested at 0.05 only, if all other 5 secondary endpoints analyses are statistically significant at 0.01.

As the analysis for time to deterioration in urinary symptoms from the QLQ-PR25 was not significant, the final analysis of OS will be conducted at the level of significance of 0.04 (2-sided). The effect of Enzalutamide+ADT compared to placebo+ADT will be tested using a log-rank test stratified by prior docetaxel use (yes versus no) and disease volume (low versus high).

The null and alternative hypotheses to be tested are as follows:

The null hypothesis: OS for Placebo+ADT and Enzalutamide+ADT are not different The alternative hypothesis: OS for Placebo+ADT and Enzalutamide+ADT are different

The following SAS code will be used to compute the Kaplan-Meier estimates and curves, and the stratified log-rank test:

PROC LIFETEST DATA=INPUT ATRISK

```
PLOTS=SURVIVAL(CB)
OUTSURV=SURVPL
ALPHA=0.04
ALPHAQT=0.04 METHOD=KM;
TIME AVAL*CNSR(1);
STRATA STRATUM/ GROUP=TREATMENT;
RUN;
where INPUT is the input dataset
```

AVAL is the time to the event variable,

CNSR is 0 (patients with events) or 1 (patients without no event, i.e. patient censored) STRATUM is the stratification variable (volume of disease and prior docetaxel use) TREATMENT is the treatment variable

Kaplan-Meier methods will be used to estimate the distribution of OS events by treatment group. The median OS will be estimated using the corresponding 50th percentile of Kaplan-Meier estimates. A two-sided 95% confidence interval will be provided for this estimate by use of the Brookmeyer and Crowley method. The 25th percentile and the 75th percentile of OS will also be provided. A Kaplan-Meier plot by treatment group will be presented. The estimates of the event free rate on a 3-monthly basis up to 1 year and every 6 months thereafter will be summarized by treatment group, as long as at least 10 patients are at risk.

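### Does placebo crossover to open-label enzalutamide undermine the stated 80% power for overall survival?

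*SAP*

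**What the plan says.** SAP section 4 sizes the OS analysis: "342 death events will be required to provide 80% power to detect a target HR of 0.73", with medians of 40 months on placebo and 55 on enzalutamide, "at the 4% significance level under the assumption of an exponential distribution". Protocol section 7.1 gives the same numbers without naming the distribution.

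SAP section 1 says the document adds summaries to "incorporate the placebo patients who crossed over to open-label enzalutamide", and section 6.3 defines a placebo crossover group with its own treatment-emergent period. Protocol section 12.6.2 describes the switch at Open-Label Day 1.

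The OS test takes no account of the switch. SAP section 5.1 analyses patients by randomized arm, "regardless of whether or not study drug was administered". Section 6.1 counts all deaths to the cut-off, and section 7.4.1 sets a stratified log-rank test at two-sided 0.04. The sensitivity analyses in section 7.4.1 name a rank-preserving structural failure time model for crossover, as something that may be used.

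Section 7.4.1 also reports the OS interim: "84 deaths from any cause, 39 in Enzalutamide + ADT group and 45 in Placebo + ADT group". Protocol section 7.4.2 had expected about 170 deaths at that point.

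**The concern.** An exponential model gives each arm one constant hazard. If placebo patients start enzalutamide part-way through follow-up, their hazard should fall towards that of the other arm, and the as-randomized hazard ratio moves towards 1. Power at a fixed 342 deaths then drops. The interim came at 84 deaths, so up to 342 − 84 = 258 deaths (75%) could fall after the unblinding that made switching possible. At the planned 170 it would have been 342 − 170 = 172 (50%).

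What is at stake is the reading of a non-significant OS result. Someone relying on section 4 would put the chance of missing the planned effect at 20%. If 0.73 describes the effect without switching, that chance is higher, and section 4 does not warn of it. Type I error is not in question.

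**Working it through.** **Reproducing the plan's figure.** Inputs from SAP section 4: HR 0.73, two-sided alpha 0.04 (z = 2.054), power 80% (z = 0.842), 1:1 allocation.

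- Schoenfeld: D = 4 × (2.054 + 0.842)² / (ln 0.73)² = 338.6 deaths. The Freedman form gives 345. The stated 342 lies between them.
- Power at 342: Φ(|ln 0.73| × √342 / 2 − 2.054) = Φ(2.910 − 2.054) = 80.4%.
- Medians: 40/55 = 0.727, consistent with 0.73.
- The O'Brien-Fleming-type spend at 84/342 deaths is about 0.00003, so the final level remains about 0.04.

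Only HR, alpha, power and allocation enter the event formula. A target of 0.73 meant as the net as-randomized effect, and a target of 0.73 meant as the effect with no switching, both lead to the same count. Reproducing 342 therefore cannot show which was meant.

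**What follows if 0.73 is the effect without switching.** None of the next inputs is in the documents; all are assumptions.

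- c: uptake among placebo patients alive at the switch
- s: death count at which switching starts
- r: hazard of switchers relative to non-switchers
- e: hazard multiplier after switching (0.73 = full effect; √0.73 = 0.854 = half the log effect)

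Formulas:

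- Switchers' share of the placebo hazard: w = c·r / (c·r + 1 − c)
- HR after the switch: 0.73 / (1 − (1 − e)·w)
- Mean log HR = [s·ln 0.73 + (342 − s)·ln(HR after switch)] / 342
- Power = Φ(|mean log HR| × √342 / 2 − 2.054)

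Worked case, c = 30%, s = 140, r = 1, e = 0.73: w = 0.30; HR after switch = 0.73 / (1 − 0.27 × 0.30) = 0.794; averaged HR = 0.767; power = Φ(2.449 − 2.054) = 65.4%.

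| Start (deaths) | Effect in switchers | r | Power at 10 / 30 / 50% uptake |
|---|---|---|---|
| 140 | full | 1 | 76.0 / 65.4 / 52.6% |
| 140 | full | 0.5 | 78.2 / 72.2 / 63.4% |
| 140 | half | 1 | 78.1 / 73.0 / 67.1% |
| 140 | half | 0.5 | 79.2 / 76.2 / 72.1% |
| 232 | full | 1 | 78.1 / 72.7 / 66.5% |
| 232 | full | 0.5 | 79.2 / 76.1 / 71.8% |

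Simulation (4,000 runs, 550 per arm) agrees closely with the formula in most full-effect cells. It falls lower at high uptake with r = 0.5: 59% against 63.4% for a start at death 140 and 50% uptake. A start at death 84 would give 74.7 / 60.5 / 43.8% (full effect, r = 1), but that is an unreachable bound, because Protocol section 12.6.2 requires site activation and allows about 16 weeks for Open-Label Day 1.

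For a start near death 140, the chance of a miss with full effect is 28–35% at 30% uptake and 37–47% at 50%. With half the log effect it is 24–27% and 28–33%. The first pair is valid only if a late start keeps the whole benefit.

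**The case for a change.** The best case for a change is that this SAP, dated July 2021, was written for the final OS analysis with crossover already known. It restates the 80% in the present tense, adds the exponential assumption, and itself refers to a crossover effect on OS. Uptake and timing are recorded in the IRT (SAP section 3.3), and "revisions to the approved SAP may be made prior to database hard lock", so two or three sentences and one calculation would settle how the 80% should be read. The structural failure time analysis does not answer the point: it is optional, and it addresses the effect estimate rather than the power of the log-rank test.

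Much of that stands. Neither document says whether 0.73 is net of switching, and if it is not, power is below 80%.

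What does not stand is the step to a failed assumption. One median per arm is a usual planning simplification; it does not assert that nobody changes therapy. The documents expect later treatment: new antineoplastic therapy is an endpoint, Protocol section 4.4.3 allows unblinding at progression to choose the next treatment, and section 1.3 reports approval of enzalutamide for metastatic castration-resistant disease in more than 100 countries. The post-docetaxel trial described in section 1.4 showed its survival effect although 61.4% of placebo patients had subsequent therapy. This does not prove that 0.73 allows for open-label switching, but a strict no-switching reading is not established.

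Nor would a reader of a negative result depend on planning power. The SAP will report the crossover group's disposition (7.2.1) and exposure (7.3.1), new antineoplastic therapy (7.2.4 and 7.4.2), and the hazard ratio with its 95% confidence interval (7.4.1). These are more informative than a recalculated planning figure.

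**Conclusion.** No change follows. The 80% in SAP section 4 and Protocol section 7.1 is correct for what it states: 80.4% power at 342 deaths for an as-randomized hazard ratio of 0.73. The gap is one of documentation, namely whether 0.73 already allows for switching.

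If it does, nothing is lost. If it does not, the loss runs from about one percentage point (10% uptake, lower-risk switchers, and either a late start or half the log effect) to nearly 28 points (50% uptake, start near death 140, equal risk, full effect: 80.4% to 52.6%). The entry rules in Protocol sections 12.6.3 and 12.6.4 point to lower-risk switchers, which favours the milder rows. Every driver of that range is assumed, so the documents cannot place the trial within it.

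Filling the gap would leave the log-rank test, the 0.04 level, the 342-death trigger and the decision rule as they are. Analysts reporting the result will have the actual uptake and the confidence interval. A sentence on whether 0.73 is net of switching, in both documents, would be a courtesy to readers; nothing in the analysis depends on it.
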